2.2 Data included in the analysis

The statistical analyses will be performed using all data collected in the database up to the data cutoff date. Any data collected beyond the cutoff date will not be included in the analysis and will not be used for any derivations.

2.3 Analysis sets

2.3.1 Full analysis set (FAS)

The Full Analysis Set (FAS) consists of all randomized patients. Following the intent-to-treat principle, patients will be analyzed according to the treatment and stratum they were assigned to at randomization.

2.3.2 Safety Set

The Safety Set consists of all patients who received at least one dose of any component of study treatment and have at least one post-baseline safety assessment. Patients will be analyzed according to the treatment actually received. Treatment actually received refers to the treatment the patient was randomized to, unless the alternative treatment was received throughout the trial. If a patient takes at least one dose of the randomized treatment then the treatment actually received is the randomized treatment. The statement that a patient has no AE constitutes a safety assessment. Occurrence of a death constitutes a safety assessment as well.

2.3.3 Cross-over analysis set

The cross-over analysis set includes all patients in the placebo arm of the Safety set, who elected to cross-over to receive ribociclib combination therapy and received at least one dose of cross-over open-label ribociclib.

2.3.4 Patient classification

Patients may be excluded from the analysis sets defined above based on the protocol deviations entered in the database and/or on specific subject classification rules as defined in [Table 2-1](#).

Table 2-1 Patient classification based on protocol deviations and non-protocol deviation criteria

Analysis set	Protocol deviations leading to exclusion	Non-protocol deviation criteria leading to exclusion
FAS	No written informed consent	NA
Safety set	No written informed consent	No post-baseline safety assessment or no dose of study treatment
Cross-over analysis set	No written informed consent	NA

Withdrawal of Informed Consent

Any data collected in the clinical database after a subject withdraws informed consent from all further participation in the trial, will not be included in the analysis data sets. The date on which a patient withdraws full consent is recorded in the eCRF.

3 Statistical methods used in reporting

3.1 Background and demographic characteristics

The FAS will be used for all baseline disease characteristics and demographic summaries and data listings.

3.1.1 Basic demographic and background data

Qualitative data (e.g., race, ECOG performance status, etc.) will be summarized by means of contingency tables by treatment arm and quantitative data (e.g., age, body weight, etc.) will be summarized by appropriate descriptive statistics (mean, standard deviation, median, minimum, and maximum) by treatment arm.

3.2 Protocol deviation summaries

The number and percentage of patients in the FAS with any protocol deviation will be tabulated by deviation category (as specified in the Study Specification Document) and by treatment arm. Additional protocol deviation summaries will be provided to address the potential impact of COVID-19 pandemic. The number and percentage of patients in the FAS with any protocol deviation with relationships to COVID-19 will be summarized by deviation category and by treatment arm.

All protocol deviations will be listed.

3.3 Groupings for analysis

The number and percentage of patients in each analysis set (definitions are provided in [Section 2.3](#)) will be summarized by treatment arm.

3.4 Patient disposition

Patient disposition for all randomized patients will be summarized based on FAS. There will be one combined by-treatment summary showing:

1. Number (%) of patients treated/untreated.
2. Number (%) of patients who are still on-treatment (based on the absence of the 'End of treatment' page)
3. Number (%) of patients who crossed over and are still on-treatment (based on the 'Crossover details' page and absence of the 'End of treatment' page)
4. Number (%) of patients who discontinued study treatment (based on the 'End of Treatment' page)
5. Number (%) of patients who crossed over and discontinued study treatment (based on the 'Crossover details' page and the 'End of treatment' page)
6. Reasons for study treatment discontinuation (based on 'End of Treatment' page)
7. Number (%) of patients who entered the post-treatment evaluations (based on 'End of Treatment' page)
8. Number (%) of patients who discontinued from the post-treatment evaluations (based on 'End of post treatment follow up disposition' page)

9. Reasons for discontinuation from the post-treatment evaluations phase (based on 'End of post treatment follow up disposition' page).
10. Number (%) of patients who entered survival follow-up.

3.5 Study treatment

Duration of study treatment exposure, cumulative dose, dose intensity (DI) and relative dose intensity (RDI) will be summarized by treatment. The number of patients with dose reductions/interruptions, and the reasons, will be summarized based on the safety set. Duration of exposure to cross-over open-label ribociclib plus fulvestrant treatment will be listed and the number of patients with dose reductions/interruptions and the reasons, will be listed based on the cross-over analysis set.

Details of the derivations and summaries are provided in the following sections.

3.5.1 Duration of study treatment exposure

The duration of exposure to study treatment will be calculated as

Duration of exposure to study treatment (days) = (last date of exposure to any study treatment component) – (date of first administration of study treatment) + 1.

Duration of exposure to ribociclib/placebo (days) = (last date of exposure to ribociclib/placebo) – (date of first administration to ribociclib/placebo) + 1.

Duration of exposure to fulvestrant (days) = (last date of exposure to fulvestrant) – (date of first administration to fulvestrant) + 1.

The last date of exposure is defined as follows for the study treatment components:

- For ribociclib /placebo: the last date of exposure is defined as the date of last administration of the corresponding medication;
- For fulvestrant, the last date of exposure is defined as following:
 1. If patient discontinues fulvestrant before C2D1 dose, then:
 - a. Last date of exposure = last date of administration + 13 days.
 - b. If patient died or lost to follow-up within last date of administration + 13 days, then last date of exposure is date of death or last contact date, respectively.
 2. If patient discontinues fulvestrant after C2D1 dose, then:
 - a. Last date of exposure = last date of administration + 27 days.
 - b. If patient died or lost to follow-up within last date of administration + 27 days, then last date of exposure is date of death or last contact date, respectively.

The duration of exposure includes the periods of temporary interruption (of any component of the study treatment for any reason). The duration of study treatment exposure will be summarized by treatment arm. In addition, the duration of exposure to study treatment will be categorized into time intervals (e.g., <3 months; 3-<6 months; 6-<9 months, etc.); frequency counts and percentages will be presented for the number of patients in each interval.

For analyses related to the cross-over on-treatment period, duration of exposure of cross-over open-label ribociclib plus fulvestrant treatment will be calculated as above considering the

combination of drugs ribociclib plus fulvestrant administered during the cross-over on-treatment period.

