2.1.5 Date of last administration of study treatment

The date of last administration of study treatment is defined as the last date when a nonzero dose of any component of study treatment was administered and recorded on the DAR CRF.

For analyses related to the cross-over period, date of last administration of cross-over open-label ribociclib plus fulvestrant treatment is defined as the last date when a non-zero dose of any component of the cross-over open-label ribociclib plus fulvestrant treatment was administered and recorded on the DAR CRF during the cross-over period.

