2.1.8 On-treatment assessment/event

Safety summaries and selected summaries of deaths will summarize only on-treatment assessments/events.

Double-blind on-treatment period:

An on-treatment assessment/event is defined as any assessment/event in the following time interval:

[date of first administration of study treatment, the earliest between the date of last administration of study treatment + 30 days and the date of first administration of cross-over open-label ribociclib plus fulvestrant treatment – 1 day], i.e., including the lower and upper limits.

The double-blind on-treatment period is the **default** on-treatment period used in the analyses unless specified otherwise.

Cross-over on-treatment period:

An on-treatment assessment/event is defined as any assessment/event in the following time interval: [date of first administration of the cross-over open-label ribociclib plus fulvestrant treatment, date of last administration of the cross-over open-label ribociclib plus fulvestrant treatment + 30 days], i.e., including the lower and upper limits.

(Note: However, the calculation of study treatment duration will use different rules as specified in [Section 3.5.1](#)).

An AE started in the screening phase and ongoing in the on-treatment phase will not be considered as an on-treatment AE unless it has worsened.

If the last date of study treatment is missing, any assessment/event occurring after the start of study treatment will be considered as on-treatment.

Data listings will include all assessments/events, flagging those which are not on-treatment.

Note: The date of first administration of study treatment and the date of last administration of study treatment are defined in [Sections 2.1.4](#) and [2.1.5](#), respectively.

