3.5.2 Cumulative dose and average daily dose

Cumulative dose for any component of study treatment is defined as the total dose of the medication given during the study treatment exposure.

Average daily dose is defined as [Cumulative dose (mg) / Number of dosing days]; drug free day(s) are not counted as dosing days.

Cumulative dose and average daily dose will be summarized using descriptive statistics by treatment arm for each component of study treatment. Patients with no exposure to the study treatment component will be excluded from the corresponding summary.

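### Does the final SAP count open-label treatment after cross-over as placebo-arm exposure?

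*SAP*

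**What the plan says.** Final SAP Section 3.5 summarises duration, cumulative dose, dose intensity and relative dose intensity by treatment. In 3.5.1 the end point of total duration is the last exposure to any component: "Duration of exposure to study treatment (days) = (last date of exposure to any study treatment component". For fulvestrant, "If patient discontinues fulvestrant after C2D1 dose, then" the last exposure date is the last administration plus 27 days. In 3.5.2 cumulative dose is "defined as the total dose of the medication given during the study treatment exposure". None of 3.5.1 to 3.5.3 names a period for the by-arm figures. The last paragraph of 3.5.1 adds a separate duration for the cross-over period.

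Section 2.1.8 ends the double-blind period at "the earliest between the date of last administration of study treatment + 30 days and the date of first administration of cross-over open-label" combination treatment, less one day, and makes it the default "on-treatment period used in the analyses unless specified otherwise". A note in the same section says that treatment duration follows the rules of 3.5.1. Section 2.1.5 defines the last administration of study treatment as "the last date when a nonzero dose of any component of study treatment was administered and recorded on the DAR CRF", and then defines a separate last date for open-label treatment.

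Switchers stay in the placebo column. Section 2.3.2 says "If a patient takes at least one dose of the randomized treatment then the treatment actually received is the randomized treatment", and the cross-over set in 2.3.3 consists of "all patients in the placebo arm of the Safety set, who elected to cross-over to receive ribociclib combination therapy".

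**The concern.** Fulvestrant is a component of treatment before and after the switch, and the SAP formulas contain no cut-off at the switch. Taken word for word, a switcher's last exposure date is then the end of open-label fulvestrant, and the patient is still tabulated under placebo. Open-label days would enter total duration and fulvestrant duration, and open-label injections would enter fulvestrant cumulative dose. The silence stands out because dose changes (3.5.4), discontinuations (3.5.5), concomitant medication (3.6), adverse events (3.7.1.3) and laboratory data (3.7.2) all state a double-blind limit or a cut at the switch.

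At stake is the placebo column of the exposure table: its mean, maximum, total patient-time and highest duration categories could be too large, next to adverse event tables with a shorter window. Two programmers might also produce different figures.

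**Working it through.** The plan gives no figure to reproduce. The check compares the sections and then sizes the literal reading.

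**1. Which period applies?**

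- Section 2.1.8 supplies a general default, the double-blind period, which ends the day before the first open-label dose. Section 3.5.1 departs from it expressly only in its cross-over paragraph.
- Section 2.1.1 defines study treatment by the two randomised combinations and gives the open-label combination its own name. Sections 2.1.2 to 2.1.5 give open-label treatment its own first and last dates. If the plain last administration date already covered open-label doses, the separate last date in 2.1.5 would be largely redundant.
- Section 3.5.1 calculates cross-over duration by the same rules applied to drugs given in the cross-over period, as a parallel quantity.
- The note in 2.1.8 also stands in Section 2.1.8 of the SAP for the primary PFS analysis (based on amendment 2), before any cross-over was planned. There it could only separate the 30-day safety tail from the exposure rules (last dose for ribociclib/placebo, plus 13 or 27 days for fulvestrant). It still does that job and need not be read as removing the cut at the switch.

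**2. Literal reading, per patient.** Illustration (cycle counts are assumptions): 52 double-blind cycles, then m open-label cycles, full fulvestrant dosing with the extra Cycle 1 Day 15 injection.

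- Stopped at the switch: last blinded injection on day 28 × 51 + 1 = 1,429; plus 27 gives 1,456 days. Dose = 500 × 52 + 500 = 26,500 mg.
- Literal: duration = 28 × (52 + m); dose = 500 × (52 + m) + 500.

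| m | Days | Excess days | Dose (mg) | Excess (mg) |
|---|---|---|---|---|
| 6 | 1,624 | 168 | 29,500 | 3,000 |
| 12 | 1,792 | 336 | 32,500 | 6,000 |
| 24 | 2,128 | 672 | 38,500 | 12,000 |

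The excess is 28 days and 500 mg per open-label cycle. Fulvestrant relative dose intensity is 1.0 either way, because the numerator and denominator grow together. For ribociclib/placebo, 3.5.1 ties the end date to the corresponding medication, so the placebo component can simply end with placebo.

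**3. Sensible reading, what is left over.** The last blinded injection counts as 28 days of exposure. The switch falls at the next scheduled visit, nominally 28 days later. With a window of ±3 days on each visit the gap is 22 to 34 days, so the overlap is max(0, 28 − gap) = 0 to 6 days.

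**4. Literal reading, arm level (assumptions throughout).** Placebo patients: 727/3 ≈ 242. Time on treatment follows the planning PFS mixture (40% with median 18 months, 60% with median 6.5), with uniform 12-month accrual. The switch comes 3 months after the amendment date, to allow for the approval and consent that protocol 4.1.2 requires. Uptake is full. This leaves 13.5 patients on treatment with no drop-out, or 7.8 with a drop-out hazard of 0.0105 per month. Nearly all are first-line, so post-switch time over a 36-month window uses a hazard of ln 2/18 = 0.0385 per month.

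- No drop-out: (1 − e^(−0.0385 × 36))/0.0385 = 19.5 months; 13.5 × 19.5/242 = 1.1 months added to the mean.
- No drop-out, hazard multiplied by 0.67 (the planning hazard ratio): 0.0258 per month gives 23.4 months; 13.5 × 23.4/242 = 1.3 months.
- With drop-out: 0.0385 + 0.0105 = 0.0490 per month gives 16.9 months; 7.8 × 16.9/242 = 0.5 months.

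Modelled mean double-blind exposure under such assumptions is 12.5 to 15.0 months. Enrolment ended in June 2016 and the amendment is dated 29 January 2020, so every switcher already has about 43.5 months or more of blinded treatment. At 13.5/242 = 5.6% of the arm, switchers are in the upper tail on either reading and the median does not move.

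**The case for a change.** The best case for acting is that the default does not clearly reach this table. The 2.1.8 note sends treatment duration to 3.5.1, and 3.5.1 has no cut. Nor is the terminology uniform: the disposition list in 3.4 speaks of study treatment for patients who crossed over, and 3.7.2 adds the word double-blinded when it means the blinded part. The by-arm text of 3.5.1 to 3.5.3 is essentially carried over from 3.6.1 to 3.6.3 of the primary-analysis SAP, which looks like an incomplete update. One sentence would settle it.

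The omission and the loose wording stand. They show a missing detail, not an instruction to pool. The 3.4 line is a count tied to the end-of-treatment page and derives no exposure date. Double reporting is also limited: final SAP 3.5 lists cross-over exposure and does not summarise it, so the SAP plans no second summary of the same days, although protocol 10.3 mentions one. Whether programmers would actually diverge cannot be judged here, because Section 1 of the final SAP places further specifications in the table shells and dataset specifications, which are not among the documents and may already contain the cut.

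**Conclusion.** No change to the plan is needed. The by-arm period is unstated in 3.5.1 to 3.5.3, but the 2.1.8 default, the separate open-label definitions in 2.1.1 to 2.1.5 and the separate cross-over calculation in 3.5.1 lead an analyst to stop at the switch. What then remains is an overlap of 0 to 6 days per switcher.

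If the literal reading were programmed, the error would be 28 days and 500 mg per open-label cycle per switcher, confined to descriptive total duration, fulvestrant duration and fulvestrant cumulative dose in the placebo column. Fulvestrant relative dose intensity hardly moves, the median is unaffected, no planned statistic divides adverse events by exposure, and no efficacy result uses these figures. The documents do not give switcher numbers or open-label time, so the 0.5 to 1.3 months is only an illustration, resting on the planning PFS mixture, a 3-month lag, full uptake and a 36-month window. The conclusion depends on the section comparison and on the descriptive role of these tables, not on that range.

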3.5.2 Cumulative dose and average daily dose

Cumulative dose for any component of study treatment is defined as the total dose of the medication given during the study treatment exposure.

Average daily dose is defined as [Cumulative dose (mg) / Number of dosing days]; drug free day(s) are not counted as dosing days.

Cumulative dose and average daily dose will be summarized using descriptive statistics by treatment arm for each component of study treatment. Patients with no exposure to the study treatment component will be excluded from the corresponding summary.

3.5.3 Dose intensity and relative dose intensity

Dose intensity (DI) for ribociclib/placebo for patients with non-zero duration of exposure to ribociclib/placebo is defined as follows:

$DI \text{ (mg / day)} = \text{Cumulative dose (mg)} / \text{adjusted duration of exposure to ribociclib/placebo (day)}$,

where *adjusted* duration of exposure (days) to ribociclib/placebo is the number of ribociclib /placebo dosing days a patient would be expected to have received per protocol, given their duration of exposure. Since ribociclib /Placebo follows a 3 weeks on, 1 week off schedule, the adjusted duration of exposure to ribociclib/placebo is the duration of exposure to ribociclib/placebo minus the planned off days for ribociclib /placebo. The adjusted duration of exposure to ribociclib/placebo (in days) is therefore $21 * (\# \text{ completed } 28 \text{ day period}) + \min(21, \text{duration of last incomplete cycle})$.

For example, if the duration of exposure to ribociclib/placebo is 66 (corresponding to two cycles and 10 days) days, then the adjusted duration of exposure to ribociclib/placebo is $21 * 2 + 10 = 52$ days. If the duration of exposure to ribociclib/placebo is 108 days (corresponding to three cycles and 24 days), then the adjusted duration of exposure is $21 * 3 + 21 = 84$ days.

Specifically, let D1 represent the duration of exposure to ribociclib/placebo as defined above. Then the adjusted duration of exposure is defined as

$D = 21 * [D1/28] + \min(21, D1 - 28 * [D1/28])$ days,

where $[x]$ stands for the integer part of x. In this equation $[D1/28]$ is the number of completed cycles, and $D1 - 28 * [D1/28]$ is the additional number of days in the last, incomplete cycle (if any). For example, if $D1 = 30$ then $[D1/28] = 1$, $D1 - 28 * [D1/28] = 2$, and $D = 23$. If $D1 = 7$ then $D = 7$; if $D1 = 22$ then $D = 21$; if $D1 = 28$ then $D = 21$, etc.

Planned dose intensity (PDI) is defined as the assigned dose by unit of time planned to be given to patients as per protocol. The PDI for ribociclib/placebo is displayed in [Table 3-1](#). Note that DI will also be calculated and DI for ribociclib/placebo will be reported in the units displayed in [Table 3-1](#), whereas duration of exposure itself will be summarized in months.

Table 3-1 **Planned dose intensity**

Medication	PDI (dose unit/unit of time)
ribociclib /placebo	600 mg/day (3 weeks on 1 week off)

Ribociclib/placebo relative dose intensity (RDI) is defined as:

$RDI = DI \text{ (dosing unit / unit of time)} / PDI \text{ (dosing unit / unit of time)}$.

Fulvestrant RDI is defined as:

$RDI = \text{actual cumulative dose} / \text{planned cumulative dose}$, where planned cumulative dose is defined as $500 * (\# \text{ completed D1 in a 28-days cycle})$ and added by 500 mg if patients completed C1D15.

DI for ribociclib/placebo and RDI for ribociclib/placebo and fulvestrant will be summarized separately for each of the study treatment.

3.5.4 Dose reductions, or interruptions

The number and percentage of patients with dose reductions, interruptions or delays, and the reasons, will be summarized by treatment arm as outlined below for double-blind on-treatment period. The dosage administration record of ribociclib will be listed by cross-over open-label ribociclib plus fulvestrant treatment for the cross-over on-treatment period.

Interruption: An interruption is defined as a 0 mg dose given on one or more days during the period where a patient is not on the “off” part of a treatment cycle, after which > 0mg dose resumes. For patients who had dose interruption checked but never resumed non-zero dose, the dose interruption will not be counted. For example, in the sequence of 600 mg – 0mg (dose break) -0mg (dose interruption) – 0 mg (dose permanently discontinuation) the 0mg (dose interruption) will not be counted as dose interruption. Interruptions will be summarized for each component of the study treatment.

Reduction: A reduction is defined as a decrease from the previous non-zero dose to another non-zero dose less than protocol planned dose, even if this decrease has been directly preceded by an interruption. For example, in the sequence of ribociclib 600mg – 0mg – 400mg, the 400mg dose will be counted as a reduction.

If due to dosing error, a patient took a dose during the dosing break with a dose that is lower than the previous dose, this will not be considered as dose reduction. For example, a patient took 600 mg from day 1-21, and mistakenly took 200 mg per day on day 22-28 which is supposed to be a dosing break. The patient resumed 600 mg dosing on day 29. This will not be considered as dosing reduction.

Dose reductions and interruptions will be tabulated separately. Dose escalations are not allowed according to the protocol and will not be counted in these summaries.

Missing data: If dose is recorded but frequency is missing or entered as ‘none’, it is assumed that the study drug was taken as per-protocol.

